- a. Study staff will contact Texas community organizations to share study information (e.g., via email). If the contacts agree to share the study’s information with individuals in their organization, we will share with them the study’s consent link and the study’s QR code for easy access. Any information shared will be currently approved language (e.g., summary of the study) and study materials (e.g., flyer, consent link). We are willing to get any special authorizations required. We will follow the policies they have in place in respect to sharing information with individuals in their organization.

Online Screening (see Appendix B)

Parents. After receiving information about the study and being presented with the online informed consent statement that covers the screening survey, intervention, and follow-up surveys, if eligible (Appendix A), individuals will be asked to complete an electronic signature before being directed to participate in the online screening survey, which will determine whether or not they are a good fit for the study. The electronic signature will be requested via a text box where participants can draw their signature. This electronic signature would include a date and time stamp. Only those participants who sign both the online consent/assent form and HIPAA Authorization Form (one for themselves; one for their child if age 15-17) will be routed to the Screening Welcome Page. The consent form will include signature boxes for parent consent for self and parent consent for their child if age 15-17. HIPAA forms will be separated for parent and for their child. Once they hit the “Next” button on the screening welcome page, they will be routed to the online screening consent survey. Participants who do not provide consent for themselves (and consent for their teen if age 15-17) as well as HIPAA authorization forms for themselves (and their teen if age 15-17) will be routed to the screening decline page and will never view the screening survey. The electronic signature will be requested via a text box where participants can draw their signature as well as type their signature. This electronic signature would include a date and time stamp.

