Please see study flow charts that demonstrate participant flow, including the consent process.

We are requesting informed consent for the screening survey, baseline, intervention, and follow-up surveys to be obtained online with an electronic signature because the entire study is administered online. The electronic signature will be requested via a text box where participants can draw their signature. Participants will provide informed consent (and assent if their child is age 15-17) for the screening survey, baseline, intervention, and follow-up surveys with electronic signatures. Parents who indicate that they are not the legal guardians of their child age 15-17 will be automatically marked ineligible and routed to the end page of the survey. Participants who decline to provide consent will be sent to the end page of the survey. For participants who do not provide consent, survey programming will skip the remainder of the survey, thus instructing them to not sign the form is not necessary. Participants who do not provide consent for themselves (and consent for their teen if age 15-17) would be moved straight to the survey end page. If a parent consents but does not complete the screening survey, they will receive up to 3 email reminders to complete the screening survey.

We will ask parents for consent for their teen (if age 15-17) for the full study (screening, baseline, and follow-up surveys) before commencing the screening survey. As such, teens age 15-17 who are eligible will have parent consent for baseline and follow-ups. Teen consent/assent will be obtained for the full study before commencing the screening survey. Thus, a separate consent form will not be signed at the beginning of each follow-up survey.

Parents will be informed in the informed consent and screening survey that in order to be eligible for the study, their child must also assent/consent to and be eligible to participate in the study.

We ask for parent contact information as a way to track their own participation as well as to track participants whose parents indicated consent or non-consent throughout the study as an additional check to only recruit

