teens with parent/guardian consent. We can program our tracking database to flag any parent contact information (email) that was previously given from parents/guardians who rescinded their consent. We also use parent/guardian contact information as a way to ensure that the parent/guardian and the teen have different email addresses. If duplicate emails are used, this is flagged in our system as part of the parent verification process and the teen will not be moved forward in the study and will receive the not eligible end survey page.

Participants Age 15-20 Full Study Assent/Consent

Please see study flow charts that demonstrate participant flow, including the consent process.

We are requesting informed consent/assent for the screening survey, baseline, and follow-up surveys to be obtained online with an electronic signature because the entire study is administered online. The electronic signature will be requested via a text box where participants can draw their signature. Participants will provide informed consent for themselves (or assent if age 15-17) for the screening survey and follow-up surveys with electronic signatures. For participants who do not provide consent, survey programming will skip the remainder of the survey, thus instructing them to not sign the form is unnecessary. Participants who do not provide consent would be moved straight to the end page. Participants will not be allowed to complete the screening survey unless their parent has already completed screening, been deemed eligible, and provided their contact information and parental consent if age 15-17.

In order to reduce participant burden, consent/assent will be obtained for the full study (if eligible) for all participants before commencing the screening survey. Thus, a separate consent/assent form will not be signed at the beginning of each follow-up survey

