Feasibility will be assessed by (1) the proportion of parents who meet inclusion criteria and enroll for the study, (2) the proportion of teens who meet inclusion criteria and enroll in the study, and (3) the proportion of parent and teens who complete the *interactive SNS PBI* at 1 month follow-up. Finally, the length of time it took to recruit our target enrollment number will also be used as an outcome of feasibility.

Acceptability will be assessed with parent and teen responses at 1 month. Acceptability will be determined by (1) the proportion of eligible parent/teen dyads enrolled, with 80% of eligible dyads agreeing to participate, (2) the proportion of participants (both parents and teens) who find the intervention acceptable (e.g., acceptability of content delivery method), usable (e.g., ease of viewing and interacting with *interactive PBI* content), relevant (e.g., relevance of material), and helpful (e.g., finding content helpful, beneficial, important), (3) parents' and teens' ratings of individual modules in the SNS PBI, (4) whether teens would like to have additional conversations on this topic, (5) whether parents would share the information in the PBI with anyone else, (6) the proportion of parents and teens who would recommend the study, and (7) the proportion of parents and teens who found the program to be favorable overall. Acceptability will be specifically determined if *acceptability for the interactive SNS PBI is higher than control and if at least 80% of responses in each domain are rated a 4 or higher (out of 5)*.

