4. *Laboratory methods and facilities* - Indicate where specific laboratory tests will be performed; e.g., hospital chemistry laboratory, investigators' laboratory, radiology clinic, etc. If None, state N/A

N/A

5. *Estimated Period of Time to Complete the Study* – Describe the stages and total time of subject participation as well as overall time for the entire study (start to completion). Also, if study involves more than one visit, describe time range estimates for each visit (e.g., 20-30 minutes; 2 – 3 hrs, etc.). Where possible, use a table or “bullet-point” format to clearly illustrate the flow of activities and procedures.

Overall time for the entire study, start to finish: 6 months

Total time of subject participation: 2 hours and 20 minutes, plus the time parents allocate for either the intervention website or the Surgeon General's Call to Action.

The brief online screening and consent should take approximately 5 minutes to complete.

The online baseline survey should take approximately 45 minutes to complete.

Intervention content will be administered during a 4-week period.

The online 1-month follow-up survey should take approximately 45 minutes to complete.

The online 6-month follow-up survey should take approximately 45 minutes to complete.

F. Human Subjects - Describe the characteristics of the research population:

1) *Sample Size*: Number of subjects to be enrolled in this study at this site. Approximately 300 (150 parents; 150 teens) subjects at 1 sites in the U.S. will be enrolled in the study overall.

For Clinical Trial studies, indicate number of subjects to be randomized 300

2) Describe both *Inclusion AND Exclusion Criteria*. BE SPECIFIC! Also, if children (persons under age 18) are excluded from this study provide scientific justification for such exclusion. Include physical, mental, cognitive, medical, and other relevant Inclusion and Exclusion criteria.

Inclusion criteria for Parents/Legal Guardians:

- 1) have a child between the ages of 15-20 who currently lives with them
- 2) believe that their child is active on at least one SNS
- 3) live in Texas
- 4) did not participate in a Phase 1 focus group
- 5) provide a valid email address
- 6) own a cell phone with text messaging capabilities and be okay with receiving messages
- 7) provide valid contact information for their teen
- 8) willing to participate in a study that involves a parenting program and a series of online surveys with their teen

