- 9) provide a valid phone number

Inclusion criteria for Teens:

- 1) have an eligible parent with whom they currently live
- 2) between the ages of 15-20
- 3) live in Texas

- 4) did not participate in a Phase 1 focus group
- 5) active on at least one SNS
- 6) provide a valid email address
- 7) own a cell phone with text messaging capabilities and be okay with receiving messages
- 8) willing to complete 3 45-minute online surveys over the course of 6 months
- 9) Note that both parent and teen must be eligible to enroll in the study.
- 10) provide a valid phone number

Eligibility questions will be embedded in other questions so as not to make the criteria obvious. Screening will be conducted to ensure the participant meets eligibility criteria and also provides age, date of birth, and unique person items. If an individual meets criteria at screening, the programmed algorithm will trigger a request to enter contact information. We will monitor individuals' personal information (e.g., home address, phone numbers, date of birth, computer IP address) to ensure that individuals cannot participate multiple times.

Exclusion criteria include not meeting inclusion criteria, unwillingness to participate, failure to provide consent (e.g., declining participation in the study), providing inconsistent responses (e.g., age and date of birth) identified by the survey, and having already participated in the study as identified by overlap or consistency in computer IP addresses, contact information, and demographics.

- 3) Describe intended *gender, age range, intended racial and ethnic distribution*. If any vulnerable subjects are involved in this study (e.g., those with limited autonomy or decision-making capabilities), justification must be provided.

We will stratify recruitment based on age, gender, and ethnicity, recruiting equal numbers of parents with adolescents in each of the age categories (i.e., 15, 16, 17, 18, 19, 20) and targeting equal numbers of males and females in each age group. We will recruit all minority parents to be above local census estimates.

- 4) Identify the *source(s) from which you will obtain your study population*.

Participants will be selected by targeted online (Facebook/Instagram/Twitter; Craigslist and online newspapers) advertisements, community organizations, schools, and in-person flyering and handouts.

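### Read literally, the eligibility rules make the 80% dyad-enrolment mark close to automatic, and the mark is settled before any family sees the intervention

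*Combined protocol and SAP*

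**What the plan says.** Section E.1 (Data Analysis and Data Monitoring) opens its acceptability paragraph with "Acceptability will be assessed with parent and teen responses at 1 month". The first criterion listed is "the proportion of eligible parent/teen dyads enrolled, with 80% of eligible dyads agreeing to participate". The paragraph closes with a separate decision rule: acceptability must be higher than in the control arm, and at least 80% of responses in each domain must be rated 4 or more out of 5. That second 80% is a different threshold.

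The stages that decide who is eligible are set out elsewhere:

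- **Online Screening (Parents).** Before screening, parents sign an "online informed consent statement that covers the screening survey, intervention, and follow-up surveys, if eligible". Those who do not consent "will be routed to the screening decline page and will never view the screening survey".
- **Participants Age 15-20 Full Study Assent/Consent.** For teens likewise, "consent/assent will be obtained for the full study (if eligible) for all participants before commencing the screening survey". A parent whose teen never answers the consent invitation or reminders is classed as ineligible.
- **Parent Full Study Consent.** Parents are told that "in order to be eligible for the study, their child must also assent/consent to and be eligible to participate in the study".
- **F.2 Inclusion and Exclusion Criteria.** A parent must be "willing to participate in a study that involves a parenting program and a series of online surveys with their teen", and teens have a matching willingness item. "Exclusion criteria include not meeting inclusion criteria, unwillingness to participate, failure to provide consent (e.g., declining participation in the study".
- **Phone Verification.** Anyone not verified after 21 days becomes ineligible. Only dyads that remain suitable and interested go on to baseline.
- **Intervention Content.** Randomization follows both baselines. The intervention link is then sent to parents in the intervention arm only.

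**The concern.** A rate of agreement among eligible dyads is informative only if an eligible dyad can still say no. Here refusal, non-consent, teen non-response and failed verification are all classed as ineligibility. Applied as written, those rules take the families who did not join out of the denominator and leave almost only those who did.

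The criterion is also filed under the wrong construct. It is complete before allocation and before anyone opens the website, so it cannot record a reaction to the intervention or differ by arm because of it.

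At stake is planning of the future trial. This is the only enrolment rate in E.1 that carries a threshold. A reported pass could suggest that families join more readily than they do, because teen refusal, non-response and verification loss would not show in it.

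**Working it through.** **Plan's own figure.** The 80% mark has no derivation, confidence rule or defined denominator, so there is no calculation to reproduce. The input is the planned 150 randomized dyads (Aim 2).

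**Order of events.** (1) Parent consents to the full study. (2) Parent is screened, including on willingness. (3) Teen consents to the full study. (4) Teen is screened, including on willingness. (5) Both are phone-verified; silence or failure means ineligible. (6) Interested dyads complete baseline, with re-consent first if the teen has turned 18. (7) Randomization. (8) Intervention link sent. (9) 1-month survey. Agreement comes at steps 1 and 3, confirmed eligibility at step 5, and the first sight of the intervention at step 8.

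**Literal reading: denominator is dyads confirmed eligible at step 5.**

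- If *agreeing* means consent, every dyad in the denominator has already consented, so the rate is 100%.
- If *enrolled* means both baselines complete, let L2 be the dyads lost between verification and baseline. The rate is 150/(150 + L2). Since 150/0.80 = 187.5, the mark passes at 187 eligible dyads (150/187 = 80.2%) and fails at 188 (150/188 = 79.8%). It tolerates 37 losses.

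**Looser reading: denominator is dyads whose parent passed the screen at step 2.** Let L1 be the dyads then lost to teen refusal, teen non-response or non-verification. The rate is 150/(150 + L1 + L2), which falls below 80% once L1 + L2 reaches 38, that is, at L1 = 38 − L2.

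| L2 (assumed) | Rate among confirmed-eligible dyads | L1 at which the parent-screen rate fails |
|---|---|---|
| 0 | 150/150 = 100% | 38 |
| 10 | 150/160 = 93.8% | 28 |
| 20 | 150/170 = 88.2% | 18 |
| 30 | 150/180 = 83.3% | 8 |
| 38 | 150/188 = 79.8% (fails) | already failed |

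As proportions, let c be baseline completion among verified dyads and r the share of parent-eligible dyads that reach verification. The parent-screen rate is r × c, with break-even r = 0.80/c. For c = 1.00, 0.95, 0.90 and 0.85 (assumed), that is r = 0.800, 0.842, 0.889 and 0.941.

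**How easily the literal version passes.** Take 187 confirmed-eligible dyads, each lost independently before baseline with an assumed probability. The mark needs at least 150 enrolled (0.80 × 187 = 149.6). The binomial chance of passing is about 1.00 for a loss probability of 0 to 10%, 0.97 at 15%, 0.51 at 20% and 0.06 at 25%.

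**Context from the documents.** Section C reports parent-consent rates of 87/93 = 93.5% (stated as 94%), 66/74 = 89.2% (stated as 89%) and 73.2%, with non-consenting parents kept in the denominator. These are parent rates, not dyad rates, and do not predict this trial. They do lie on both sides of 80%, so the choice of denominator could decide the result.

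**The case against.** The criterion's own wording presupposes that an eligible dyad can decline. Aim 2 counts eligible participants separately from consenting parents and teens. The Online Screening text for ages 15-20 treats a parent as eligible before the teen is contacted, and separates a teen who declines from one who is not eligible. On that reading the mark is an ordinary uptake rate that can be missed. This stands: the literal reading is not the only one. But E.1 does not choose between the two, and the exclusion list supports the literal one.

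A reader might infer that the mark cannot fail. The documents do not support that: even on the literal reading it fails once 38 dyads are lost before baseline, if enrolment means both baselines complete. No loss rate is given, so it cannot be said how likely that is.

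A reader might also infer that recruitment losses would be hidden altogether. That goes too far. Aim 2 promises consent counts and E.1 promises recruitment and retention rates. Teen refusal and non-response together could be recovered from these. Verification losses would appear only mixed with other ineligibility.

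It can also be said that joining a study described as a parenting program carries some information on anticipated acceptability. That is fair, but it concerns the offer, not the intervention, which no family has yet seen.

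Finally, the protocol refers to study flow charts for participant flow and consent. They could not be consulted, nor could the pages between the start of the compensation schedule and the reference list. Either might fix the stages.

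**Conclusion.** The concern holds as a minor point. Under the protocol's own rules, confirmed eligibility already contains agreement. The 80% mark is then 100% if it means consent, and depends only on verification-to-baseline losses if it means both baselines complete (pass up to 187 eligible dyads, fail at 188). The looser use of *eligible* in other sections gives a lower rate from the same record. All loss figures above are break-evens on assumed values; the actual gap between the readings is unknown.

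Independently of the denominator, the rate is settled before randomization and intervention access, so it does not belong with 1-month acceptability.

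Two further inferences are not supported. The pilot's acceptability decision is not undermined, because the closing rule does not use this mark, and no randomized comparison is affected. Nor is the parent-screen rate a floor covering every refusal: parents who decline at consent, or who state unwillingness at screening, fall outside it.

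Confidence is moderate, given the material that could not be consulted.

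**What to change.** In E.1:

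1. Move the 80% mark from acceptability to recruitment feasibility.
2. Define *enrolled* as both baselines complete and the dyad randomized.
3. Set the denominator as dyads whose consenting parent passes the parent screen, excluding duplicate entries and teens found factually ineligible.
4. Count as not enrolled: teen refusal, withdrawal or missing re-consent before baseline, and missed baseline.
5. Report the rate with and without teen non-response and non-verification.
6. Report parents who decline at consent, or who state unwillingness at screening, as separate counts.
7. State that the ineligible label for teen non-response and for failed verification ends participation but does not remove the dyad from this denominator. If the flow charts already fix these stages, cite them instead.

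The cost is wording plus one tally. Consent status is stored, and data on consenting eligible and ineligible people are kept (Consent Documents; Future Research Opportunities). Contact details of teens who refuse or do not respond are to be deleted within 120 days after the study ends, so each dyad's de-identified outcome should be tallied before then. The reported rate will be lower and shown as a range. Refusing or silent teens will be counted on their parent's account of the facts, which should be noted beside the rate.

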Aim 2: Conduct a pilot study with parents and their adolescents aged 15-20 from the Dallas/Fort Worth (DFW) area to determine feasibility, acceptability, and preliminary effect sizes (to estimate power and sample size for a future R01 application). Parent/teen dyads (N=150 dyads for a total of 150 parents and 150 teens) will be randomized to interactive PBI (n=75 dyads) or active control (n=75 dyads) with a 1- and 6-month follow-up. Parents in the interactive PBI condition will receive the interactive web-based SNS PBI with text message prompts developed and finalized through Aim 1 focus groups. Parents in the active control condition will receive an emailed copy of the Surgeon General's Call to Action: A Guide for Families. General Hypotheses (parent and teen). *We hypothesize that the interactive SNS PBI will be feasible* (i.e., number of eligible participants, number of parents who gave consent, number of teens who gave consent, length of time to achieve planned recruitment and enrollment goal, rate of study completion and rate of study attrition)

and acceptable (i.e., proportion of parents and teens who find the intervention acceptable; ease of viewing and interacting with interactive PBI content; relevance of material; finding content helpful, beneficial, important; ratings of individual web-based modules and text messages of the PBI; the proportion of parents and teens who would recommend the study to other families, and the proportion of parents and teens who found the interactive PBI to be favorable overall) relative to active control. We further hypothesize that teens and parents in the interactive PBI condition will report more positive communication about alcohol and SNS at the 1- and 6-month follow-up relative to active control. *Parent Hypotheses:* We hypothesize that at 1- and 6-month follow-up, parents in the interactive PBI condition will report greater knowledge about alcohol as well as the role of SNS in alcohol use relative to active control. *Teen Hypotheses:* We hypothesize that teens in the interactive PBI condition will report less drinking, fewer alcohol-related negative consequences, less favorable attitudes toward posting about alcohol on SNS, greater perceived vulnerability to the risks of posting alcohol displays on SNS, and decreased normative perceptions about how many teens post alcohol displays on SNS relative to active control at 1- and 6-month follow-up.

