Parent/teen dyads who meet inclusion criteria and pass phone verification will be emailed and texted a baseline survey link. The baseline survey will include questions about demographics, social media literacy, parenting, drinking and drug use, drinking cognitions, mental health, and other health behaviors and will take approximately 45 minutes to complete. Questions in the assessments will also include topics about sexual orientation, gender identity, religion, and relationship status. For those in the Intervention group, items in the 1-month follow-up survey will assess satisfaction with the intervention website. If we do not receive the completed assessment at each follow-up (Baseline Assessment, 1-month, and 6-month assessment), we will periodically send reminders – via email (up to 8), text (up to 8) and/or phone/voicemail (up to 5). Parents and teens can earn \$25 for baseline, \$35 for the 1-month follow-up, \$40 for the 6-month follow-up, meaning that all participants can earn up to \$100.

Baseline Assessment, 1-Month, and 6-Month Measures.

While the baseline, 1-month, and 6-month surveys will contain overlapping content, we may decide to include or exclude a measure over the course of the study, with IRB approval via a modification. Thus we are electing to not indicate in the consent form that the three surveys will be the same. Overlap in surveys is indicated by the overall content areas of surveys that are provided in the consent form. Behavior will be reported over lifetime

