friends' attitudes towards toward drinking and marijuana use ($\alpha = .70\text{-.93}$; [name] et al., 2010; LaBrie et al., 2010). Perceived vulnerability will be assessed by asking participants how likely they think it is that certain alcohol consequences will happen to them ($\alpha = .82$; Gerrard et al., 2008; [name] & Stock, 2011). Prototypes will be measured by items that assess how favorable participants feel toward the typical drinker of the same sex and age ($\alpha = .87$; Gerrard et al., 2002, 2006). Experience of alcohol use will consist of one indicator of several key variables (i.e., age at first drink, quantity, frequency, perceived close friend alcohol use, and perceived access to alcohol). The willingness measure will assess willingness to use alcohol in certain scenarios ($\alpha = .85$; Gerrard et al., 2002, 2008). Intentions for alcohol use will be assessed by items on intended frequency and quantity ($\alpha = .83$; Ajzen, 2006; Gerrard et al., 2006). Perceived access to substance use will be assessed with a modified version of The Perceived Access to Alcohol and Other Drug Scale ($\alpha = .86$; Kuntsche et al., 2008). Anxiety and depression will be measured using the PROMIS Anxiety v1.0 and PROMIS Pediatric Anxiety v1.1 Short Form ($\alpha = .96$; Cella et al., 2010) and the PROMIS Depression and PROMIS Pediatric Depression v1.1 Short Form instruments ($\alpha = .96$; Cella et al., 2010), respectively.

Lastly, both parents and teens in the intervention group will be asked to complete a 1 month satisfaction scale related to their experience, perceptions, and interactions with the intervention website.

1. Data Analysis and Data Monitoring –

In order to evaluate the pilot study in Phase 2 (Aim 2), we will examine (a) recruitment and retention rates,(b) parent post-intervention feedback as measured at 1 month follow-up (i.e., accessible, usable, convenient, relevant, and helpful),(c) teens' rates of alcohol initiation and use, alcohol-related negative consequences, attitudes toward posting about alcohol on SNS, perceived vulnerability to the risks of posting alcohol displays on SNS, and normative perceptions about how many teens post alcohol displays on SNS, d) parental knowledge and attitudes toward alcohol and SNS, and e) parent and teen report of alcohol and SNS related communication which will provide base rates and variance in outcomes to determine adequate power for a future clinical trial R01 application.

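### The acceptability rule compares the PBI with control, but the plan describes no control-arm ratings and gives no summary, margin or interval for 'higher'

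*Combined protocol and SAP*

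**What the plan says.** Aim 2 in section A hypothesises that the PBI will be acceptable against the comparator; its list of acceptability measures ends with "the proportion of parents and teens who found the interactive PBI to be favorable overall) relative to active control". Allocation is 1:1, with dyads "randomized to interactive PBI (n=75 dyads) or active control (n=75 dyads) with a 1- and 6-month follow-up".

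Section E.1 turns this into a decision rule. On timing it says "Acceptability will be assessed with parent and teen responses at 1 month". It lists seven indicators, including "the proportion of participants (both parents and teens) who find the intervention acceptable", usable, relevant and helpful. The verdict is stated as "Acceptability will be specifically determined if *acceptability for the interactive SNS PBI is higher than control and if at least 80% of responses in each" (the scale point needed per domain is 4 or more out of 5). The 80% part is a number. The comparative part is the word 'higher' alone. The text does not say whether it refers to a composite or to each domain, or to parents, teens or both.

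The mixed models described next in section E.1 use three repeated measures. They are named for teen drinking, consequences and cognitions and for parent knowledge, not for acceptability.

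On data collection, the section Baseline Assessment, 1-Month, and 6-Month Assessments says "For those in the Intervention group, items in the 1-month follow-up survey will assess satisfaction with the intervention website". The measures section closes by saying that "both parents and teens in the intervention group will be asked to complete a 1 month satisfaction scale related to their experience" and their use of the intervention website. The available text describes no matching items for control families.

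**The concern.** Only the 'higher than control' condition carries the Aim 2 claim relative to active control. The 80% mark is absolute and cannot show a relative advantage. Two things are missing from the comparative condition.

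- **Data.** The described scale is about the intervention website and goes to one arm. On the text available, the comparison cannot be computed.
- **A decision standard.** If control ratings were collected, any positive difference would satisfy the condition, however small. A chance difference could then be reported as greater acceptability in support of the planned R01. Adding control items alone would not cure this, and defining the comparison alone would not supply the data.

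**Working it through.** **Plan's own figures.** The plan states no alpha, margin, SD, expected rate or attrition for this comparison, so there is no stated figure to reproduce. The only checkable arithmetic is 75 + 75 = 150 dyads.

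**Assumptions.** Control ratings exist; all 75 parents (or all 75 teens) per arm respond; the true share *p* rating 4 or more is equal in both arms. The values of *p* are mine.

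**One summary, one respondent group, equal programs.**

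- Mean score treated as continuous: by symmetry P(PBI higher) = 0.50.
- Share rating 4+: X and Y are independent Binomial(75, *p*). By symmetry P(X > Y) = (1 − P(X = Y))/2. At *p* = 0.85 this is (1 − 0.0914)/2 = 0.454.
- Full one-domain rule: P(X > Y and X ≥ 60), because 0.80 × 75 = 60.

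| True share, both arms | P(tie) | P(higher) | P(80% mark met) | P(full one-domain rule) |
|---|---|---|---|---|
| 80% | 0.082 | 0.459 | 0.569 | 0.382 |
| 85% | 0.091 | 0.454 | 0.911 | 0.452 |
| 90% | 0.109 | 0.446 | 0.997 | 0.446 |
| 95% | 0.152 | 0.424 | 1.000 | 0.424 |

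With 60 raters per arm the last column is 0.382, 0.445, 0.439 and 0.415, so fewer responders change little.

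**PBI truly 5 points worse, full one-domain rule, 75 per arm.** 80% against 85% gives 0.170; 85% against 90% gives 0.145.

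**Other readings of 'higher', true 85% in both arms.**

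- Higher in every one of four domains, plus the 80% mark in each, one respondent group. I simulated 20,000 trials per setting, dichotomising correlated normal ratings. The rule passes 0.042, 0.076, 0.104 and 0.173 of the time at inter-domain correlations of 0, 0.3, 0.5 and 0.8.
- One domain, with parents and teens both required and treated as independent: 0.452 × 0.452 = 0.204.

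**What an interval rule would do.** For a mean score in SD units, SE = √(2/75) = 0.163. The lower limit of a two-sided 90% CI exceeds 0 when the observed difference exceeds 1.645 × 0.163 = 0.269 SD. The chance of that is Φ(d/0.163 − 1.645):

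- d = 0: Φ(−1.645) = 0.05
- d = 0.3: Φ(1.837 − 1.645) = Φ(0.192) = 0.576
- d = 0.5: Φ(3.062 − 1.645) = Φ(1.417) = 0.922

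**The case against.** The strongest reply is that this is a pilot. It aims at feasibility, acceptability and preliminary effect sizes, and a descriptive comparison beside an absolute threshold is a defensible progression criterion. That stands as far as a powered test goes; none is needed. It does not excuse leaving the compared quantity undefined, or stating the comparison as a condition of the verdict when no control measure is described.

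Three stronger readings are tempting, and the documents do not support them.

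- A reader might infer that the trial as planned would call a no-better-liked PBI acceptable about half the time. It would not: on the described data collection the comparison cannot be made at all. The near-half rate applies only after control ratings are added, and only for one summary in one respondent group. Grammatically the per-domain wording attaches to the 80% mark, which favours a single comparison, but the plan does not settle it. Other readings give about 4 to 20% at a true 85%.
- A reader might infer that the 80% mark offers no protection. At a true 80% a single domain meets it only 57% of the time. At 85%, all four domains in one group meet it about 69 to 78% of the time in the same simulation. It screens out little only from about 90% upward.
- A reader might infer that a slightly less liked PBI passes about a quarter of the time. That figure (27%) needs a deficit of 0.1 SD on a continuous score the plan never defines, and it ignores the 80% mark. On the plan's own 4-or-higher scale, a 5-point deficit passes 15 to 17% of the time.

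The survey appendices and a few protocol pages were not available, so control-arm items there cannot be excluded.

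**Conclusion.** The point holds in a limited form. The acceptability verdict depends on a comparison for which the available text describes no control-arm data and defines no summary, margin or interval.

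If matching ratings were collected and 'higher' were read as one summary in one group, equally acceptable programs would satisfy it about 42 to 50% of the time. With the 80% mark included, the one-domain rate is about 38% at a true 80% and 42 to 45% at 85 to 95%. The spread down to about 4% under other readings is itself a consequence of the rule being undefined.

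These rates rest on 75 raters per arm, equal true rates and, for four domains, assumed correlations. The absolute 80% criterion is not in question. This is a worthwhile and inexpensive correction, not a threat to the trial's validity.

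**What to change.** Make two linked changes.

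1. **Data collection.** Reconcile the assessment and measures sections with section E.1, so that parents and teens in both arms answer the same general acceptability items at 1 month, worded for the material each family received. Ratings of individual PBI modules stay in the PBI arm. If the appendices already contain such control items, say so in the main text.

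2. **Decision rule.** In section E.1, replace the words 'is higher than control' with text such as:

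> The PBI-minus-control difference in mean 1-month acceptability rating on the shared items will be reported with a 90% confidence interval, separately for parents and teens. The PBI will be called more acceptable than control for a group only if the lower limit for that group exceeds 0. Otherwise only the absolute 80% result will be claimed.

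**Cost.** A few extra survey items for control families, one interval per respondent group, and no added participants. The comparative claim becomes harder to make: with 75 raters per arm the observed difference must reach about 0.27 SD, and the chance of making the claim is about 58% for a true 0.3 SD advantage and 92% for 0.5 SD. In return, the chance of the claim when there is no difference falls to 5% per group.
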